7.4.2. Additional issues in genomic data analysis

Data from microarray datasets or other -omics technology datasets will follow standard manufacturer protocols for data generation. To obtain high quality measurements, we will use software that is considered standard for each platform, with a publication record to support its use. Examples include GCRMA (Wu et al, 2004) for Affymetrix expression arrays, or several packages in R/Bioconductor for expression analysis and genotype calling. The potential for batch effects will be considered and handled via regression methods for clinical site, as well as further correction for modest batch effects that may only be apparent from projections of high-dimensional data to low dimensions. We will employ global batch effect correction procedures such as ComBat (Johnson et al, 2007).

For simple exploratory analyses of genomic data we will employ standard two-way cluster analysis and dimensional reduction techniques (such as principal components) to visualize -omics expression measurements and provide initial views of the data structure. We will also employ iterative techniques, such as tight clustering (Tseng & Wong Biometrics, 2005), and randomization approaches designed to test the strength of cluster relationships. Pairwise correlation matrices will be examined across the genes (or a filtered set) and across arrays to identify unexpected features that are not reflected in the clustering. In certain analyses we will act to reduce the weight of genes that have high correlation with other genes, so as to appropriately reduce the influence of highly correlated groups of genes/samples that may otherwise dominate the final clustering. Grouping of genes with various profiles will also be accomplished using Self-Organizing Maps and graphed using various software packages. We will employ standard software for analysis of microarrays and other -omics platforms. Examples of the standard software include Treeview/Cluster, Genespring, and JMP Genomics. A variety of pathway analysis procedures will also be employed, including Gene Set Enrichment Analysis, SAFE, SAFE-GUI, GoMiner, and GenMAPP.

Genomics data are often highly multivariate, and the complicated data structures enable “sharing” of information across portions of the data to improve the power of hypothesis testing. For differential expression analysis, we will employ Significance Analysis of Microarrays (SAM) or similar software, which applies a shrinkage factor to penalize the significance of genes with low expression. Empirical Bayesian techniques can have similar effects to increase power for detecting significant genes in microarray experiments, compared to standard significance testing. For error rate control, resampling methods will be employed to identify statistically significant relationships in -omics data while controlling for numerous hypothesis tests, while reflecting covariance relationships in the data without explicit modeling. Among the simplest examples are controlling Type I (false-positive) error in the discovery of differentially expressed genes, or the discovery and characterization of genetic pathways correlated with clinical parameters. Analysis of genetic association data also greatly benefits from this approach, because positive correlation among hypothesis tests is very common, and thus approaches such as the Bonferroni correction may be unacceptably conservative. Bootstrap methods resample with replacement, and are thought to better represent draws from the alternative hypothesis (if indeed the alternative holds). Both permutation and bootstrapping will be used to control family-wise error rates and false discovery rates (FDR). Permutation methods for controlling the FDR have advantages in precise error control. Error control will be provided via the Benjamini-Hochberg step-down procedure when parametric tests are used and permutation is not feasible (e.g. when the sample size is too small). Cross-validation will also be performed in assessing prediction accuracy for complicated statistical models where standard theory may not apply. Key considerations include the relative proportions of the data to be used for training models and testing them, and whether it is more important to estimate the relevant quantities (such as prediction error) with little bias or little variance.

The data gathered in SPIROMICS may include single nucleotide polymorphism (SNP) genotypes, perhaps in candidate genes or regions suggested by other studies**. Association mapping of clinical outcomes will be carried out using individual SNP testing approaches, as well as simple haplotype-based approaches augmented by SNP imputation using the MACH software (Scott et al., (2007) Science 316:1341-1345). The statistical models to be used will depend on the type of data representing the trait of interest. For example, for a binary trait, such as presence or absence of a clinical biomarker, logistic regression or a chi-square test may be used. For ordinal or time-to-event responses, such as disease severity or time to first exacerbation, multinomial regression or a proportional hazard/odds model will be performed. For continuous traits, such as lung density or lung function, simple linear regression will be performed. Significance of results will employ permutation-based testing as described above to control family-wise error and false discovery rates.

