3.2. Secondary Aims

3.2.1. Secondary Aim 1: Cohort Building

Recruit, enroll, and maintain the SPIROMICS cohort to support longitudinal evaluation, ancillary studies, and possible enrollment in concurrent clinical trials.

Thirty-two hundred (3,200) participants will be recruited and enrolled at six clinical centers into four strata (non-smokers, smokers, mild/moderate COPD, severe COPD). Participants will be equally distributed between males and females and will be representative of the national racial/ethnic populations. A variety of data will be collected for each participant including physiological, radiographic, biological, and quality of life indicators. In addition to meeting the primary objectives outlined above, the maintenance of this extremely well-characterized cohort will provide valuable information about the progression of COPD and the various factors underlying this progression as well as identification of subpopulations that may be interested in participating in future therapeutic clinical trials. Contacting potential participants will be governed by the informed consent process, described more fully in Section 5.3.

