5.3. Participant Selection and Withdrawal

5.3.1. Inclusion/Exclusion Criteria

The 3,200 participants will be distributed across four enrollment strata (i.e., Non-smokers, Smokers without COPD, Mild/Moderate COPD, and Severe COPD) as shown in Table 1. Participants must fall into one of the four categories described in Table 1 in addition to meeting the inclusion/exclusion criteria described Section 5.3.1, 5.3.1.1, and 5.3.1.2 in order to be included in the study. With regards to race/ethnicity, sites' recruitment will reflect national racial distributions. All centers will recruit equal numbers of males and females.

Table 1. SPIROMICS Enrollment Strata

	Non-Smokers (Stratum 1)	Smokers (Stratum 2)	Mild/Moderate COPD (Stratum 3)	Severe COPD (Stratum 4)
Smoking Status	< 1 pack-year	> 20 pack-years	> 20 pack-years	> 20 pack-years
Bronchodilator Status for Assessing Lung Function	Pre-bronchodilator	Post- bronchodilator	Post-bronchodilator	Post-bronchodilator
FEV ₁ /FVC ratio criteria	FEV ₁ /FVC > .7	FEV ₁ /FVC > .7	FEV ₁ /FVC < .7	FEV ₁ /FVC < .7
Other Lung Function Criteria	FVC>LLN	FVC>LLN	FEV ₁ > 50% pred.	FEV ₁ < 50% pred.
Sample Size	N = 200 (6.25%)	N = 900 (28.13%)	N = 1500 (46.88%)	N = 600 (18.72%)

Regarding participation in other studies:

1. Participants may participate in concurrent observational studies, excluding the COPDGene Study (COPDGene Investigators, 2010)
2. Participants in therapeutic clinical trials can be included after the treatment is unmasked.
3. Participants in ongoing, open-label clinical trials can be enrolled if the participant is in the control group of such a study.
4. Participants recruited into SPIROMICS can be recruited into other interventional studies after SPIROMICS baseline values are obtained. Clinic staff will maintain records documenting activity in interventional studies.

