The second approach to subgroup finding posits that individualized therapies based upon a patient’s genotype are possible. DNA collection followed by either genome-wide association or specific genetic tests combined with statistical analyses will allow us to evaluate this hypothesis and to continue to unravel the correlation between underlying genetics and resultant phenotypes. Several genes have been recently reported to be associated with COPD phenotypes (see, e.g., Wood, Tan, and Stocklye, 2009 *Genome Medicine* 1:112). Concurrently run studies (e.g., the COPDGene Study (COPDGene Investigators, 2010)) will add to this list, and SPIROMICS will

be valuable in validating newly emergent findings from these studies. An example of a specific hypothesis under this approach is:

- SPIROMICS participants with SNPs previously associated with FEV₁ decline (CHRNA3/5, EPHX1, GSTP1, and HHIP) will have faster rates of decline in FEV₁ over three years than participants without those SNPs.

The third approach to subgroup finding suggests that components of COPD syndrome can be prospectively identified that are associated with a worse prognosis, as measured by morbidity over a 3-year period, when compared to participants without those components. There are many specific examples of this general hypothesis, including the following:

- Participants with apical emphysema at baseline will have more exacerbations resulting in a hospitalization over three years than those without apical emphysema.

Hypothesis #2 – Intermediate Outcome Identification: This general hypothesis can more specifically be stated as: SPIROMICS will identify intermediate outcome measures that predict long-term clinical endpoints of morbidity. Such outcomes may be markers of short-term change (1 year) that predict long-term change (3 years), or they may be markers that change with exacerbations and are predictive of more severe long-term morbidity/mortality.

For example:

- The novel molecular methodologies employed in SPIROMICS (including T-RFLP, phylochips, and deep-sequencing) will provide candidate markers that correlate with more frequent exacerbations and are therefore predictive of long-term morbidity/mortality.

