7.4.1.1. Subgroup Identification Procedures

Subgroup identification procedures will proceed under the assumption that most univariate clinical measurements have already been examined for potential correlation with outcome and potential utility in trial design. However, the utility of ensembles of measurements, along with new genomic and radiological measurements, is unknown. Thus we will proceed with techniques that are designed for high-dimensional settings, initially performing subgroup identification only within measurement “type” (e.g. clinical).

A basic tool for subgroup identification is hierarchical cluster analysis, for which we will perform agglomerative clustering using average linkage and correlation metrics. The identification of significant clusters (i.e. subgroups) can be a difficult task, although for parametric Gaussian cluster analysis the use of criteria such as Akaike Information can be used to determine the number of clusters when the sample size exceeds the number of observations. Bayesian approaches can also be used here, with probability-based model selection techniques and Bayes factors used to distinguish between models with different cluster sizes. Recently the SigClust procedure (2008) has been introduced for testing for cluster significance when the number of observations exceeds the sample size, and we will apply the procedure for high-dimensional measurement types.

A second technique is principal component analysis, which (for mean centered data) essentially follows from singular value decomposition of the data matrices. The use of principal

components to identify subgroups and control for stratification is a mature area in genomic analysis, and we will use similar ideas in SPIROMICS. A key aspect of principal components analysis lies in testing the significance of eigenvalues, and we will use the approach detailed in Patterson et al. (2006) to consider the number of eigenvectors/PCs that should be considered in subgroup identification.

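### The SNP association tests in Protocol 7.4.2 are specified without the stratification control that 7.4.1.1 mentions for subgroup finding, so in a racially mixed cohort they are open to confounding by ancestry.

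*Protocol*

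**What the plan says.** Protocol 7.4.2 matches a model to each trait type for SNP association.

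- Continuous traits: "For continuous traits, such as lung density or lung function, simple linear regression will be performed".
- Binary traits: "logistic regression or a chi-square test may be used".
- Ordinal and time-to-event traits: "multinomial regression or a proportional hazard/odds model will be performed".
- Significance: "Significance of results will employ permutation-based testing as described above to control family-wise error and false discovery rates".

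No covariate is named for any of these models, and nothing restricts the permutation by ancestry.

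The cohort is racially mixed by design. Section 5.3.1 says that "recruitment will reflect national racial distributions", and section 3.2.1 says that participants "will be representative of the national racial/ethnic populations".

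Stratification appears once, in section 7.4.1.1. There the use of principal components to "control for stratification is a mature area in genomic analysis, and we will use similar ideas". That paragraph is about subgroup identification, and the eigenvalue test that follows serves to choose components for that purpose.

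Section 7.3 makes genotype one of three approaches to subgroup finding under a co-primary hypothesis. Its example is that carriers of SNPs in "CHRNA3/5, EPHX1, GSTP1, and HHIP" lose FEV₁ faster over three years.

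**The concern.** In ordinary usage a simple linear regression has one predictor, and a chi-square test takes no covariates. If a SNP's allele frequency differs between ancestry groups and the trait mean also differs between them, an unadjusted test picks up the ancestry difference along with any genotype effect. The result can be a false association, or a true one masked when the two run in opposite directions.

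The permutation step looks like a safeguard but is not one here. Shuffling the trait freely breaks its link with ancestry as well as with genotype. The reference distribution therefore describes a population without confounding, while the observed statistic still contains it. Permutation controls multiplicity across SNPs; it does not remove this bias.

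At stake is the genotype-based route to subgroups. Section 7.3 also offers the study as a place to validate genetic findings from concurrent studies. A signal driven by ancestry could mislead both that validation and any targeted enrolment built on it.

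**Working it through.** **Where adjustment is stated and where it is not**

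- 7.4.1: measurements used for subgroup finding are first regressed on covariates such as age, gender, height, weight and design stratum. Race and ancestry are not named.
- 7.4.1.1: principal components and stratification, for subgroup identification.
- 7.4.2, array data: regression on clinical site, for batch effects.
- 7.4.2, SNP tests: no covariates named.
- 7.4.3: intermediate outcomes are regressed on gender, height, weight and site. Race and ancestry are not named.

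So the protocol names adjustments elsewhere, and none of them reaches the SNP tests.

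**Illustration of size.** The protocol gives no error rate or power for the SNP tests, so there is no figure to reproduce.

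Inputs from the protocol:

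- n = 3,200 for the whole cohort.
- n = 1,711 COPD participants with Year 3 FEV₁, from the mortality and retention assumptions in 7.1: 1,500 × 0.90 × 0.92 + 600 × 0.85 × 0.92 = 1,242 + 469.2 = 1,711.
- Two-sided alpha of 0.05 (7.1). The 0.001 level is the one 7.1 uses for testing many surrogates; it serves here only as an example of a stricter threshold.

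Assumed, not in the documents: share in a second ancestry group f = 0.20; allele frequencies p1 = 0.20 and p2 = 0.40; trait gap d = 0.2 within-group SD; no SNP effect.

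Formulas, with G the allele count and T the trait:

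- Cov(G,T) = f(1−f) × 2(p2−p1) × d = 0.16 × 0.4 × 0.2 = 0.0128
- Var(G) = (1−f)·2p1(1−p1) + f·2p2(1−p2) + f(1−f)·4(p2−p1)² = 0.256 + 0.096 + 0.0256 = 0.3776
- Var(T) = 1 + f(1−f)d² = 1.0064
- corr = 0.0128 / √(0.3776 × 1.0064) = 0.02076
- z = corr × √n; rejection = 1 − Φ(c − z) + Φ(−c − z), with c = 1.960 at alpha 0.05 and 3.291 at alpha 0.001

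| n | z | Rejection at 0.05 | Rejection at 0.001 |
|---|---|---|---|
| 3,200 | 1.175 | 0.217 | 0.017 |
| 1,711 | 0.859 | 0.138 | 0.008 |

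Range at n = 3,200 and alpha 0.05, keeping f = 0.20 and p1 = 0.20: a frequency gap of 0.1 with a trait gap of 0.1 SD gives 0.061; gaps of 0.3 and 0.3 SD give 0.711.

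**Simulation.** The central case at n = 3,200 (4,000 replicates) rejected 0.210 unadjusted and 0.052 after ancestry adjustment. A second case included permutation: n = 2,100 (the COPD strata), a 20% share, allele frequencies 0.30 and 0.50, a gap of 0.2 SD, 1,000 replicates with 199 permutations each.

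| Test at nominal 0.05 | False-positive rate |
|---|---|
| Unadjusted regression | 0.141 |
| Unrestricted permutation | 0.140 |
| Ancestry-adjusted | 0.053 |

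With the trait gap set to zero, the unadjusted test stayed at 0.050. Bias needs both gaps.

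**The case against.** The strongest reply is that the authors plainly know about population stratification. Section 7.4.1.1 names the standard tool and cites a paper on population structure and eigenanalysis to choose the number of components. A reader might infer from 7.4.2 that the study plans no ancestry control of any kind; 7.4.1.1 does not support that. What stands against the plan is narrower: that control is tied to subgroup identification and is not linked to the SNP tests.

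Second, section 7.3 defers detail to an analysis plan for each hypothesis, and covariate lists commonly belong there. That would excuse silence. It does not undo a stated choice of simple regression, which such plans would inherit. The word could be loose, since the same paragraph also speaks of simple haplotype approaches, but one predictor is its ordinary meaning.

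Third, the binary-trait wording is permissive and offers logistic regression, and the ordinal and time-to-event models can take covariates. This stands: only the continuous-trait model is fixed as simple regression. SNP genotyping is itself conditional in 7.4.2.

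Fourth, the size rests wholly on assumed inputs, and the 5% figures are per SNP before multiplicity control. This also stands. The named hypothesis concerns decline in FEV₁, and the documents give no ancestry difference in decline. At 0.001 the central rates are small in absolute terms, though still roughly 8 and 17 times nominal.

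**Conclusion.** The point holds as a weakness in a stated method. Followed as written, 7.4.2 tests SNPs against continuous traits without ancestry adjustment, allows an unadjusted test for binary traits, and relies on permutation that does not remove confounding, in a cohort meant to mirror the national racial mix.

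A reader might go further and conclude that ancestry differences will be reported as genotype effects. The documents do not support that: bias arises only where allele frequency and trait mean both differ by ancestry, and they give neither difference, nor the ancestry shares. Under the assumptions shown, the per-SNP false-positive rate at nominal 5% is about 22% (n = 3,200) or 14% (n = 1,711), with a range at 3,200 from about 6%, close to nominal, to 71%. At alpha 0.001 the central case gives about 1.7% and 0.8%. These figures show that the effect can matter, not how large it will be. They cover false positives only; masking follows from the same mechanism but was not quantified.

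**What to change.** In 7.4.2, replace simple linear regression and the chi-square test with regression models suited to the trait (linear, logistic, ordinal or proportional hazards) that include ancestry principal components. If only candidate SNPs are typed, use ancestry-informative markers or self-reported race instead. State that permutation respects this adjustment, either by permuting residuals or by permuting within ancestry group. A cross-reference from 7.4.2 to the principal components in 7.4.1.1 would make the link explicit.

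The cost is mainly wording, since 7.4.1.1 already accepts the principle. The one downside is that, with candidate SNPs only, self-reported race or a marker panel adjusts less completely than components from dense genotyping, and a panel means extra typing. Other covariates, such as smoking or site, are a separate question that this point does not settle.

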7.4.3. Intermediate Outcome Identification and Initial Validation

Validating biomarkers or surrogate endpoints is quite challenging, especially if the goal is to satisfy the Prentice criteria for surrogate validity (Prentice, 1989). The Prentice criteria demand two conditions of a surrogate S for a primary endpoint T : (1) that S and T be correlated (i.e., not independent) and (2) that a test of the null hypothesis of no treatment effect on S is equivalent to a test of the null hypothesis of no treatment effect on T . In applying the Prentice criteria,

candidate surrogates are first screened relative to condition (1) by examining the correlation between the candidate surrogates and clinical endpoints of interest. The primary clinical endpoints in SPIROMICS are all-cause mortality, exacerbations, and decline in FEV₁, over three years. In addition, baseline measures such as initial FEV₁ will be used as secondary measures for surrogate candidate discovery. At the second stage, a test of condition (2) is carried out. With novel surrogate candidates, such as those anticipated for SPIROMICS, sets of completed clinical trials are likely not available. The approach planned here is to view differences among disease severity categories and controls as analogues of treatment group differences, and proceed with screening candidate surrogates using the methods of Daniels and Hughes (1987) for condition (2). The design of SPIROMICS is observational, involving no randomized conditions. Thus any findings of association between clinical endpoints and candidate surrogates will not establish causality of disease severity on the biomarker (or vice versa). However, association of a potential surrogate (or changes in the surrogate) with clinical endpoints occurring prospectively in the study will offer powerful evidence of the potential utility of the surrogate for future trial design.

The identification and validation process consists of a two-part screening step in which each of a pool of intermediate outcomes is examined for (a) correlation with respect to the four study design strata defined above and (b) correlation with the clinical endpoints assessed after three years of follow-up. For step (a), the term “correlation” will refer to any association between the intermediate outcome and the design strata, with no order restrictions. For step (b), it is generally understood that the most useful relationships between surrogates and clinical endpoints are monotone, therefore test statistics that are powerful for evaluation of monotone relationships are favored. Intermediate outcomes are handled as univariate measures, such as change from baseline to Year 1 values of a continuous measurement or presence/absence of a biological or clinical marker assessed at Year 1. Each intermediate outcome will be regressed on baseline covariates thought *a priori* to be important predictors, including, gender, height, weight, and clinical site. Linear models will be used for both continuous and dichotomous outcomes to produce residuals, which form the basis for the correlation tests. Least squares estimation will be employed at this step, because the focus is on examining correlations between the residuals and disease severity, after adjusting for baseline covariates, and not on prediction. The model residuals for the pool of intermediate outcomes will then be analyzed for significant trends with respect to design stratum using permutation to control the family-wise error rates for the number of potential surrogates (Westfall and Young, 1993). This approach will keep the entire set of residuals intact, permuting with respect to the clinical endpoints, and benefit from any positive correlation among intermediate outcomes in order to avoid overly stringent significance thresholds.

Candidate markers will also be identified based on previous studies or findings in the literature and considered for evaluation in SPIROMICS. Methods such as examining signal-to-noise ratios will be employed for this evaluation. For example, decline in lung density measured by computed tomography (CT) has been shown to track disease progression in emphysema patients (Stolk, et al., 2007). The signal-to-noise ratio for lung densitometry was found to be 2.5-fold that of decline in lung function or gas diffusion based on 144 COPD patients followed over 30 months.

8. Data Handling and Record Keeping

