Another targeted approach to subgroup finding corresponds to prospectively identifying components of COPD syndrome that are associated with a worse prognosis, as measured by morbidity over a 3-year study period, when compared to participants without those components. The longitudinal study design allows an evaluation of subgroups defined at baseline or during the first year of follow-up with respect to long-term outcomes such as number and severity of exacerbations and decline in FEV₁.

The statistical analysis plan for evaluation of this aim is described in greater detail in Section 7,

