that the three-year mortality was approximately 25% for patients with FEV₁ in the range 30%-39% , and approximately 13% for those with FEV₁>50%. More recently Celli et al. (2004) reported approximately 18% three-year mortality for patients with FEV₁>36% and 30% for patients with FEV₁<36%. We conservatively power the SPIROMICS study to detect a difference in all-cause mortality, assuming a 15% rate for Severe patients versus 10% for Mild/Moderate patients. With 1,500 patients in the Mild/Moderate COPD stratum vs. 600 patients in the Severe COPD stratum, we will have 88% power for this comparison.

For the TORCH study, the annual rate of exacerbations was 1.13 per participant for placebo versus 0.85 for combination therapy. In a computer model of COPD progression based on literature surveys, Borg et al. (2004) assumed an average annual rate of moderate to severe exacerbations of approximately 1.05 among COPD patients with GOLD status I/II, and a rate of 2.05 for exacerbations among COPD patients with GOLD status III. We conservatively power the SPIROMICS study to detect a difference in annual exacerbation frequency between the Mild/Moderate and Severe COPD strata, assuming an annual rate of 1.0 in the Mild/Moderate COPD stratum vs. a rate of 1.5 in the Severe COPD stratum. Using simulation and assuming a simple Poisson log-likelihood ratio test for difference in individual counts of exacerbations in the two strata and assuming 92% retention in both strata, we obtain power in excess of 95% to detect the differences.

For decline in FEV₁, the TORCH study found differences in change from baseline FEV₁ values of 0.092 (L) between the combination therapy group and placebo (95% CI = [0.075, .108]) (Calverley et al, 2007). With the proposed disease severity subgroup sample sizes and assuming attrition due to mortality ranging from 10% in the Mild/Moderate stratum to 15% in the Severe stratum, and 92% retention in those surviving in each strata, we would have approximately 95% power to detect a difference of 0.20 times the standard deviation in FEV₁ change from baseline values (using a two-sample t-test on baseline vs. Year 3 FEV₁ in the two strata).

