From the earlier conservative mortality assumptions, we expect 240 (11%) or more all-cause mortality events among the 2100 COPD patients during the course of SPIROMICS. For tests of direct association of potential surrogate endpoints/markers with this outcome, we consider for simplicity a dichotomized surrogate endpoint with relative frequency 0.50 for each value of the surrogate. In order for surrogate endpoint to demonstrate promising utility for further prospective validation in the context of a clinical trial, we propose that the surrogate confer an odds ratio of 1.8 or more. The correlation structure of the potential surrogates is not known a priori, so we use a significance level of 0.001 in order to account for multiplicity of testing (corresponding to a Bonferroni correction for 50 tests). Under these assumptions and assuming retention of 92%, a contingency table test of mortality vs. the surrogate will have 77% power to reject the null hypothesis.

7.2. *Interim Study Progress Reports*

7.2.1. *Steering Committee Reports*

Monthly management reports are prepared by the GIC and provided to the Steering Committee for monitoring of study progress. Tables and figures summarizing enrollment, completion of study procedures and visits, and baseline characteristics are included.

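### Year 1 markers are screened against three-year endpoints that start at baseline, so the two windows overlap, and the 77% power for mortality holds only for a baseline marker

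*Protocol*

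**What the plan says.** Section 7.3 states Hypothesis 2 in these terms: "Such outcomes may be markers of short-term change (1 year) that predict long-term change (3 years"), or markers that change with exacerbations and foretell worse long-term morbidity or mortality.

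Section 7.4.3 makes this operational. "Intermediate outcomes are handled as univariate measures, such as change from baseline to Year 1 values of a continuous measurement" is one example of an intermediate outcome. The other is presence or absence of a marker at Year 1. Step (b) correlates each with clinical endpoints assessed after three years of follow-up. On those endpoints the section says: "The primary clinical endpoints in SPIROMICS are all-cause mortality, exacerbations, and decline in" FEV1, over three years. Section 7.1 takes FEV1 decline as baseline against Year 3. The covariates named for adjusting the marker are gender, height, weight and clinical site.

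For power, Section 7.1 says "we expect 240 (11%) or more all-cause mortality events among the 2100 COPD patients during the course of SPIROMICS", which follows from "assuming a 15% rate for Severe patients versus 10% for Mild/Moderate patients". It considers "a dichotomized surrogate endpoint with relative frequency 0.50 for each value of the surrogate", an odds ratio of 1.8, a significance level of 0.001 and 92% retention, and concludes that "a contingency table test of mortality vs. the surrogate will have 77% power to reject the null hypothesis".

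For Primary Aim 1, Section 3.1.1 adds: "The longitudinal study design allows an evaluation of subgroups defined at baseline or during the first year of follow-up", with respect to long-term outcomes.

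**The concern.** A marker built from the Year 1 visit does not exist until that visit, yet the endpoint clock runs from baseline. The first of the three outcome years therefore lies inside the marker window. This has three separate consequences.

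- **Exacerbations.** An event in Year 1 can shift the marker and is also counted in the endpoint. The association then runs from event to marker.
- **FEV1 decline.** The changes from baseline to Year 1 and from baseline to Year 3 subtract the same baseline reading, so its error enters both.
- **Mortality.** Someone who dies before the Year 1 visit has no marker value. That death cannot enter the test, although the planned power counts it.

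Hypothesis 2 is co-primary, and its results are meant to inform trials for regulatory approval. A screen that passes markers of past events or of shared error would send the wrong candidates forward. The permutation control in 7.4.3 does not guard against this, because the correlations are real and not due to chance.

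**Working it through.** **1. The plan's 77%.** Inputs from 7.1: 1,500 × 0.10 + 600 × 0.15 = 240 deaths among 2,100, a risk of 11.43%; N = 2,100 × 0.92 = 1,932, or 966 per marker level; OR 1.8; two-sided alpha 0.001. Splitting 11.43% equally to give OR 1.8 yields risks of 8.51% and 14.35%. The two-proportion test with pooled variance has power 77.1%. The stated figure is right for its inputs, which include every death over three years (240 × 0.92 ≈ 221).

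**2. The same test for a Year 1 marker.** Let d1 be the deaths before Year 1. Then N = (2,100 − d1) × 0.92 and the risk is (240 − d1)/(2,100 − d1). The documents give no timing of deaths, so the share in Year 1 is an assumption.

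| Share of the 240 in Year 1 | d1 | N | Later deaths × 0.92 | Risk | Power at OR 1.8 | OR for 77% |
|---|---|---|---|---|---|---|
| 15% | 36 | 1,899 | 188 | 9.88% | 68% | 1.89 |
| 20% | 48 | 1,888 | 177 | 9.36% | 64% | 1.92 |
| 25% | 60 | 1,877 | 166 | 8.82% | 60% | 1.96 |
| 33% | 80 | 1,858 | 147 | 7.92% | 52% | 2.04 |

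A constant hazard within each stratum puts about 83 deaths in Year 1 and gives about 51%. The retention factor does not already cover this: for FEV1, 7.1 applies 92% to survivors, and the 77% keeps the full 11.43% risk after retention.

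**3. Exacerbations.** Assume one common Poisson rate for everyone and a marker that correlates 0.2 with the Year 1 count and is unrelated to later events. The Year 1 count correlates √(1/3) = 0.577 with the three-year count, so the marker correlates 0.2 × 0.577 = 0.115 with the three-year count and 0 with the count for Years 2 and 3. By the Fisher z approximation, the chance of passing at two-sided p<0.001 is:

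- three-year count, N = 2,100: about 98%
- three-year count, N = (1,500 × 0.90 + 600 × 0.85) × 0.92 ≈ 1,711 retained survivors: about 93%
- count after Year 1: about 0%, the nominal 0.1% rate

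**4. FEV1.** Let each reading carry independent error with SD s, and let the change from baseline to Year 1 be error only. The covariance of (e1 − e0) with (e3 − e0) is s². With no variation in true slopes, each change has variance 2s², so r = s²/2s² = 0.50. If slopes over the following two years vary with SD b per year, r = s²/√[2s²(2s² + 4b²)]. For s from 80 to 113 ml and b from 40 to 60 ml/year, r runs from 0.34 (s = 80, b = 60) to 0.45 (s = 113, b = 40). Only 113 ml comes from the Protocol (6.4.1.1, short-term reproducibility). Treating it as a within-person SD is an assumption, as are the other SDs.

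Restarting decline at the Year 1 reading reverses the sign. The covariance of (e1 − e0) with (e3 − e1) is −s², so r = −0.50 with no slope variation and about −0.34 to −0.45 with the same assumed SDs.

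**The case against.** The strongest reply is that 7.1 does not date its surrogate. Baseline levels are in scope: 7.4.1.1 predicts endpoints from baseline measurements, and 7.4.3 speaks of a surrogate or of changes in it. A reader might infer that the 77% is miscalculated and should be replaced. The documents do not support that. It is correct for a baseline marker, and it lacks only a statement of which markers it covers. The 240 is also a floor. Applying mortality figures cited in 7.1 (13% and 25%) to the two strata gives 195 + 150 = 345 deaths, and the Year 1 marker power becomes 74% or 81% with one third or one quarter of deaths in Year 1. The 25% is quoted for FEV1 of 30% to 39% only, so this is an illustration. Excluding people with an illness expected to be fatal within three years (Table 2) may also lower the Year 1 share. All this stands, which is why the power loss is given as a range.

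Second, the exacerbation example assumes no link between Year 1 and later events. If rates differ between people, the link is real: with a gamma-Poisson model, assumed shape 1 to 2 and mean rate (1,500 × 1.0 + 600 × 1.5)/2,100 = 1.14 per year, Year 1 and later counts correlate about 0.61 to 0.44. A marker of Year 1 events would then carry some prognostic information. But counting only later events would still detect it, whereas the three-year count cannot tell it from a marker that predicts nothing. Section 5.3.1.2 also defers visits for six weeks after an exacerbation. That reduces acute shifts in the marker but not lasting ones.

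Third, 7.3 promises detailed analysis plans for each hypothesis, and the screen is preliminary. Both are true. Still, the Protocol itself fixes the three-year window and gives only Year 1 examples, and no passage sets a later start.

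**Conclusion.** The concern holds, with limits. As written, step (b) of 7.4.3 lets a Year 1 marker be tested against an outcome that partly precedes it.

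- **Exacerbations:** a marker that merely reacts to Year 1 events can pass. The 93% to 98% figure rests on the assumed correlation of 0.2 and a homogeneous rate.
- **FEV1:** the induced correlation is at most 0.50, and about 0.34 to 0.45 under the assumed SDs. It affects FEV1 change and measures whose error correlates with FEV1 on the same day. A reader might extend it to every marker, but one with independent error, such as a plasma assay, is not affected by this route.
- **Mortality:** a reader might infer that early deaths also create false surrogates. They do not, because those participants have no Year 1 value and leave the test. The effect is on power alone: about 68% to 52% if 15% to 33% of 240 deaths fall in Year 1, and higher if deaths exceed 240.

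A reader might also see the same error in 3.1.1. That section fixes no start for the outcome, so it needs clarification only.

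**What to change.** 1. In 7.3 (Hypothesis 2) and 7.4.3 step (b), state that for any marker using Year 1 data only deaths and exacerbations after the Year 1 visit count, among participants alive and with a marker value at that visit.
2. For FEV1 decline, use decline after Year 1. For FEV1-based markers, and those sharing FEV1's same-day error, use a joint slope model or readings that do not overlap, because restarting at the Year 1 reading gives a spurious correlation of up to −0.5.
3. In 7.1, keep the 77% but label it as applying to markers measured at baseline. Add that for Year 1 markers power is about 68%, 64%, 60% or 52% if 15%, 20%, 25% or 33% of the 240 deaths fall in Year 1, with the timing named as an assumption, or that 77% needs an odds ratio of about 1.9 to 2.0.
4. In 3.1.1, clarify that the same rule applies to subgroups that use first-year data.

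The cost is wording, no new data collection, and a less favourable power figure. Year 1 events drop out of the Year 1 marker analyses; baseline-marker analyses keep the full three years.
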